5.4.4 Management of Pneumonitis/ILD Related to Enfortumab Vedotin

Severe, life-threatening or fatal pneumonitis/interstitial lung disease (ILD) have occurred in patients receiving enfortumab vedotin. Monitor patients for signs and symptoms indicative of pneumonitis/ILD such as hypoxia, cough, dyspnea or interstitial infiltrates on radiologic exams. For recommendations regarding dose modifications for pneumonitis/ILD due to enfortumab vedotin, refer to [Section 5.2.3](#).

5.5 Treatment Compliance

Study drug administration will be performed by study site staff and documented in source documents and the CRF.

6 STUDY ACTIVITIES

6.1 Schedule of Events

Adverse events and concomitant medications will be recorded from Day 1 (predose) through the safety reporting period (30 days after the last study treatment, see [Section 7.7.1.3](#)). Day 1 is the first day of treatment with study drug in each cycle. Any study protocol-related AE (defined in [Section 7.7.1.1](#)) as well as any concomitant medications given for treatment of the adverse event, should be recorded from the time of informed consent. A schedule of events is provided in [Appendix A](#). Study activities are listed by visit in this section and descriptions of all study assessments are presented in [Section 7](#).

Local laboratory testing should be performed on all dosing days. All local laboratory results must be reviewed prior to study drug administration in order to determine whether to proceed with dosing or whether dose modification is required.

6.2 Screening Visit (Days –28 to Day 1)

- Informed consent
- Study eligibility per inclusion/exclusion criteria
- Medical history (see [Section 7.1](#))
- Acquire and submit tumor specimen (see [Section 7.4.2](#)). Either archival tissue or pre-treatment fresh tumor tissue (obtained from a fresh biopsy) is acceptable.

- Complete eye examination (see [Section 7.7.7](#))
- Brain scan (magnetic resonance imaging [MRI] with gadolinium preferred; if contraindicated, see [Appendix F](#)) to determine eligibility with respect to CNS metastases)
- Bone scan
- CT scan with contrast (if contraindicated, see [Appendix F](#)), including chest, abdomen, and pelvis. Other regions should be scanned if the patient has known or suspected disease in that region.
- INR/prothrombin time (PT) and partial thromboplastin time (PTT)
- Serology for hepatitis B surface antigen and antihepatitis B core antibody
- Serology for antihepatitis C antibody. If positive, follow up with PCR testing.
- Urinalysis (with reflexive microscopy)
- HbA1c. If HbA1c is elevated ($\geq 6.5\%$), refer patient to appropriate provider during Cycle 1 for glucose management.

6.2.1 Baseline Visit (Days –7 to Day 1)

- Pregnancy test (either serum or urine) for females of childbearing potential (see [Section 7.7.2](#))
- Physical exam (including weight; see [Section 7.7.3](#))
- Collect height
- Vital signs (see [Section 7.7.4](#))
- Complete blood count (CBC) with differential (see [Section 7.7.2](#))
- Serum chemistry panel (see [Section 7.7.2](#))
- CrCl (see [Section 7.7.2](#))
- ECOG performance status (see [Section 7.7.5](#))
- Electrocardiogram (ECG) (see [Section 7.7.6](#))

6.3 Treatment Period (Day 1 to Day 22)

6.3.1 Day 1 (± 2 days)

- Predose (to occur on day of dosing unless noted below)
 - QLQ-C30 (see [Section 7.6.1](#))
 - EQ-5D (see [Section 7.6.2](#))
 - Pregnancy test (either serum or urine) for females of childbearing potential
 - Physical exam (including weight; may be conducted the day prior to dosing)
 - Vital signs
 - CBC with differential (may be collected the day prior to dosing)
 - Serum chemistry panel (may be collected the day prior to dosing)
 - ECOG performance status (may be conducted the day prior to dosing)

- Blood samples for PK assessments (within 24 hours prior to dose; Cycles 1–4 and every even-numbered cycle thereafter; see [Table 3](#))
- Blood samples for ATA assessments (within 24 hours prior to dose; Cycles 1–4 and every even-numbered cycle thereafter; see [Table 3](#))
- Blood samples for biomarker assessments (within 24 hours prior to dose; Cycles 1–4; see [Table 3](#))
- Enfortumab vedotin administration (see [Section 5.2.2](#))
- Postdose
 - Blood samples for PK assessments (Cycles 1–2; see [Table 3](#))

If Baseline Visit activities occur within 1 day prior to Cycle 1, Day 1, the following assessments do not need to be repeated at the Cycle 1 Day 1 visit: physical exam (including weight), vital signs, ECOG performance status, serum chemistry panel, and CBC with differential. If the baseline pregnancy test occurs within 7 days prior to Cycle 1 Day 1, the pregnancy test does not need to be repeated at the Cycle 1 Day 1 visit.

6.3.2 Day 3

- Blood samples for PK assessments (\pm 24 hours; Cycles 1 and 2)
- Blood samples for biomarker assessments (\pm 24 hours; Cycle 1)

6.3.3 Day 8 (+2 days)

- Predose (to occur on day of dosing unless noted below)
 - Vital signs
 - CBC with differential (may be collected the day prior to dosing)
 - Serum chemistry panel (may be collected the day prior to dosing)
 - Blood samples for PK assessments (within 24 hours prior to dose; Cycles 1 and 2)
 - Blood samples for biomarker assessments (within 24 hours prior to dose; Cycle 1)
- Enfortumab vedotin administration. At least 1 week must elapse between doses of enfortumab vedotin.
- Postdose
 - Blood samples for PK assessments (Cycles 1 and 2)

6.3.4 Day 15 (+2 days)

- Predose (to occur on day of dosing unless noted below)
 - Vital signs
 - CBC with differential (may be collected the day prior to dosing)
 - Serum chemistry panel (may be collected the day prior to dosing)
 - Blood samples for PK assessments (within 24 hours prior to dose; Cycles 1 and 2)
 - Blood samples for biomarker assessments (within 24 hours prior to dose; Cycle 1)

- Enfortumab vedotin administration. At least 1 week must elapse between doses of enfortumab vedotin.
- Postdose
 - Blood samples for PK assessments (Cycles 1 and 2)

6.3.5 Day 17

- Blood samples for PK assessments (-24/+48 hours; Cycles 1 and 2)

6.3.6 Day 22

- Blood samples for PK assessments (Cycles 1 and 2 [\pm 48 hours])
- CT scan with contrast (if contraindicated, see [Appendix F](#)) of the chest, abdomen, pelvis and any other region of known or suspected disease (every 8 weeks [\pm 1 week] from Cycle 1 Day 1 during treatment, with repeat scans 4 weeks [$+1$ week] after first documentation of response). Brain and/or bone scans should also be repeated at this timepoint if metastases were identified at baseline, or if metastasis is suspected. After 1 year on study the frequency of scans will be reduced to every 12 weeks (\pm 1 week). Following confirmation scans, response assessments should continue with the previous scan schedule (i.e., the schedule should not be adjusted). If there is a dose delay due to toxicity, the schedule for response assessments will not be adjusted and will continue to be timed from Cycle 1 Day 1 during treatment. Tumor imaging should also be performed whenever disease progression is suspected.

6.4 End of Treatment Visit (30 to 37 days after last dose of study drug)

EOT visits should occur 30 to 37 days after the last dose of study drug unless delayed due to an AE. However, EOT evaluations must be performed before initiation of a new therapy for cancer, with the exception of the slit lamp examination. If EOT evaluations are completed before 30 days after the last study treatment, the patient will be contacted 30 to 37 days following the last treatment to assess for adverse events.

- QLQ-C30
- EQ-5D
- Slit lamp examination (for patients who experience corneal adverse events during the study). Performed \geq 4 weeks from last dose.
- Pregnancy test (either serum or urine) for females of childbearing potential
- Physical exam (including weight)
- Vital signs
- CBC with differential
- Serum chemistry panel
- ECOG performance status
- ECG
- Blood samples for PK and ATA assessments
- Blood samples for biomarker assessments

- CT scan with contrast (if contraindicated, see [Appendix F](#)) of the chest, abdomen, pelvis and any other region of known or suspected disease. Responses will be confirmed with repeat scans at 4 weeks after first documentation of response (+1 week). Following confirmation scans, response assessments should continue with the previous scan schedule (i.e., the schedule should not be adjusted and should all be timed every 8 weeks [± 1 week] from Cycle 1 Day 1 during treatment). Tumor imaging should also be performed whenever disease progression is suspected. Bone and/or brain scans should also be repeated at this timepoint if metastases were identified at baseline, or if metastasis is suspected. Scans not required if previous scan conducted <4 weeks prior to EOT.

6.5 Every Month for 6 Months After End of Treatment Visit (± 1 week)

- Pregnancy test (either serum or urine) for females of childbearing potential

6.6 Follow-up (Every 8 Weeks [± 1 week])

Prior to initiation of subsequent anticancer therapy or radiologically-confirmed disease progression (per investigator according to RECIST), patients will have the assessments listed below done 8 weeks (± 1 week) after the previous response assessment scan and every 8 weeks (± 1 week) following the previous visit thereafter until radiologically-confirmed disease progression (per investigator according to RECIST), initiation of a new anticancer therapy, patient death, study closure, or withdrawal of consent, whichever comes first. After 1 year on study the frequency of visits including response assessments will be reduced to every 12 weeks (± 1 week).

- Physical exam
- ECOG performance status
- CT scan with contrast (if contraindicated, see [Appendix F](#)) of the chest, abdomen, pelvis and any other region of known or suspected disease (with repeat scans 4 weeks [$+1$ week] after first documentation of response). Brain and/or bone scans should also be repeated at this timepoint if metastases were identified at baseline, or if metastasis is suspected. Following confirmation scans, response assessments should continue with the previous scan schedule (i.e., the schedule should not be adjusted). Tumor imaging should also be performed whenever disease progression is suspected.

6.7 Long-term Follow-up (Every 8 Weeks [± 1 week])

After initiation of subsequent anticancer therapy or radiologically-confirmed disease progression (per investigator according to RECIST), patients will be contacted every 8 weeks (± 1 week) after EOT (or 8 weeks from previous protocol visit, whichever is later) for survival status and collection of subsequent anticancer therapy information until death, study closure, or withdrawal of consent, or patient is lost to follow-up, whichever occurs first. After 1 year on study, the frequency of contacts will be reduced to every 12 weeks (± 1 week).

6.8 End of Study/End of Follow-up

The study will be closed 5 years after enrollment of the last patient, or when no patients remain in long-term follow-up, whichever occurs first. Additionally, the sponsor may terminate the study at any time.

The date the patient met criteria for study discontinuation and the reason for study discontinuation will be recorded.

7 STUDY ASSESSMENTS

7.1 Screening/Baseline Assessments

Only patients who meet all inclusion and exclusion criteria specified in [Section 4](#) will be enrolled in this study. Enrollment status and date will be recorded in CRF.

Patient medical history includes a thorough review of significant past medical history, current conditions, tobacco history, any treatment for prior malignancies and response to prior treatment, and any concomitant medications.

A complete eye examination, brain scan, bone scan, CT scan with contrast for baseline response efficacy assessment, INR/PT/PTT, serology for hepatitis B and C, urinalysis with reflexive microscopic analysis, HbA1c, and pregnancy test (either urine or serum, for females of childbearing potential) are required for all patients at screening.

7.2 Response/Efficacy Assessments

Measures of anticancer activity will be assessed by CT scans with contrast approximately every 8 weeks (± 1 week). After 1 year on study, response assessments will be reduced to every 12 weeks (± 1 week). The schedule of response assessments should not be adjusted for dose delays/interruptions or other reasons for changes in the timing of a patient's study activities; timepoints for response assessments should be calculated from Cycle 1 Day 1 during treatment. For patients who cannot receive CT scans with contrast, other acceptable imaging methods are detailed in [Appendix F](#) (Scanning and Contrast Guidelines). For brain scans, MRI with gadolinium is the preferred method of assessment; however, other imaging methods are detailed in [Appendix F](#) if contrast is contraindicated. Patients must be evaluated using the same imaging method throughout the study for efficacy assessments. CT scans with contrast at the minimum will include the chest, abdomen, and pelvis. Other regions should be scanned if the patient has known or suspected disease in that region. Brain and/or bone scans should also be repeated at response assessment timepoints if bone metastases were identified at baseline, or if metastasis is known or suspected. Responses (CR or PR) will be confirmed with repeat scans 4 weeks (+1 week window) after first documentation of response. The schedule for response assessments should not be adjusted after the confirmatory scan (e.g., CR at Week 8, confirmatory scans at Week 12, next assessment due at Week 16). Tumor imaging should also be performed whenever disease progression is suspected.

Patients who discontinue study treatment for reasons other than objective disease progression by RECIST Version 1.1 (see [Appendix D](#)) will continue to receive CT scans with contrast

8 weeks (± 1 week) after the previous response assessment scan and every 8 weeks (± 1 week) following the previous scan thereafter. After 1 year on study the frequency of response assessments will be reduced to every 12 weeks (± 1 week). The tumor assessments will continue until the patient has radiologically-confirmed disease progression per RECIST as determined by the investigator, initiates a new anticancer therapy, dies or withdraws consent, or the study closes, whichever comes first. The determination of antitumor activity will be based on confirmed objective response assessments as defined by RECIST Version 1.1 (see [Appendix D](#)) ([Eisenhauer 2009](#)). Patients who do not have at least 2 (initial response and confirmation scan) post-baseline response assessments will be counted as non-responders. The investigator will make treatment decisions based on site assessments of scans by RECIST. Clinical response of CR, PR, SD, or PD will be determined at each assessment. Response and progression will also be assessed by an IRF.

Survival status will be updated every 8 weeks (± 1 week) after EOT (or 8 weeks from previous protocol visit, whichever is later) until death, study closure, or withdrawal of consent, whichever occurs first. After 1 year on study the frequency of survival status updates will be reduced to every 12 weeks (± 1 week).

Patients' clinical data must be available for CRF source verification. Tumor images will be submitted to a central imaging lab.

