Measures of anticancer activity will be assessed by radiographic tumor imaging at protocol-specified timepoints. Tumor response will be assessed locally and centrally by an IRF according to RECIST v1.1 (Eisenhauer 2009). Clinical response of CR, PR, SD, or PD will be determined at each assessment. Responses (CR or PR) will be confirmed with repeat scans at least 4 weeks after first documentation of response. Tumor assessments will continue until the subject has radiologically-confirmed disease progression per RECIST v1.1 by the investigator, initiates a new anticancer therapy, dies, withdraws consent, or the study closes, whichever comes first.

Safety assessments will be based on the information collected through the safety surveillance process and will include the data from recorded AEs including serious adverse events (SAEs), recording of concomitant medication, medical history, physical examination findings, and laboratory tests.

[figure not shown]
Approximately 200 subjects will be enrolled in this study, including approximately 100 or more platinum-treated subjects (Cohort 1) and up to approximately 100 platinum-naïve and cisplatin-ineligible subjects (Cohort 2).

On a periodic basis, approximately every 3 months until all treated subjects in Cohort 1 have had the opportunity to be followed for at least 6 months and at a frequency considered adequate based on the rate of enrollment to Cohort 2 thereafter, an independent data monitoring committee (IDMC) will monitor the safety of subjects participating in this trial. The IDMC will be guided by an independent charter and will be responsible for evaluating the results of safety analyses and will make recommendations to the sponsor. The IDMC may also request efficacy data, if needed, to evaluate risk/benefit before making

recommendations. The IDMC will make recommendations to either continue the study unchanged, modify the study, or discontinue the study. The final decision to act on the IDMC recommendations will be made by the sponsor.

An ongoing real-time review of subject safety and SAEs will also be conducted by the sponsor's Drug Safety Department.

Figure 1 Study Schema

^a There are 2 cohorts of CPI-treated patients in the study: Cohort 1) platinum-treated patients, and Cohort 2) platinum-naïve/cisplatin-ineligible patients.

^b After 1 year on study, the frequency of response assessments will be reduced to every 12 weeks (±1 week).

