7.5.3 Duration of Response

DOF is defined as the time from the date of first documented response (CR or PR that is subsequently confirmed) to the date of first documented PD per RECIST v1.1 or death due to any cause, whichever comes first.

DOF will be censored as described below:

- Subjects who do not have PD and are still on study at the time of an analysis will be censored at the date of the last adequate response assessment documenting absence of PD
- Subjects who have started a new anticancer treatment (with the exception of palliative radiotherapy on a non-target lesion that is not progressing) prior to documentation of PD will be censored at the date of the last adequate response assessment prior to start of new treatment
- Subjects who discontinue from the study prior to documentation of PD will be censored at the date of the last adequate response assessment documenting absence of PD.

DOF per IRF will only be calculated for subjects achieving a confirmed CR or PR per IRF. DOF will be analyzed using Kaplan-Meier methodology and Kaplan-Meier plots will be provided. The median DOF and its two-sided 95% CI will be calculated. In addition, the DOF at 6 and 12 months will be summarized.

Sensitivity Analysis

The following sensitivity analysis will be performed for the DOF per IRF:

1. A sensitivity analysis to censor subjects who progressed or died after an extended loss to follow up (i.e., ≥ 2 consecutive missed response assessments) at the date of the last adequate response assessment prior to the missed visits.

DOF per investigator will be analyzed in the same way as the DOF per IRF.

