7.5.5 Progression-free Survival (PFS)

PFS is defined as the time from start of study treatment to first documentation of PD per RECIST v1.1 or death due to any cause, whichever comes first.

The same censoring rules as outlined in Section 7.5.3 for DOR will be applied to PFS. In addition, subjects who are not known to have died and do not have any post-baseline response assessment will be censored at the date of first dose.

PFS per IRF will be analyzed using Kaplan-Meier methodology and Kaplan-Meier plots will be provided. The median PFS and its two-sided 95% CI will be calculated. In addition, the 6- and 12-month PFS rates will be summarized.

Sensitivity Analysis

The following sensitivity analysis will be performed for the PFS per IRF:

1. A sensitivity analysis to censor subjects who progressed or died after an extended loss to follow up (i.e., ≥ 2 consecutive missed response assessments) at the date of the last adequate response assessment prior to the missed visits.

PFS per investigator will be analyzed in the same way as the PFS per IRF.

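### DOR and PFS per IRF can be biased upward because scans stop at investigator-called progression, and the planned sensitivity analysis cannot show it

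*Protocol*

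**What the plan says.** **When scans stop.** Protocol 7.2 ends tumor assessments at "radiologically-confirmed disease progression per RECIST as determined by the investigator", at a new anticancer therapy, or at death, withdrawal of consent or study closure. Protocol 6.6 has the same rule, and so does SAP 4: "Tumor assessments will continue until the subject has radiologically-confirmed disease progression per RECIST v1.1 by the investigator". After that, Protocol 6.7 provides contacts "for survival status and collection of subsequent anticancer therapy information", without imaging. One exception is possible: Protocol 6.4 lists a CT at the end-of-treatment visit, 30 to 37 days after the last dose and before new therapy, waived if a scan was done less than 4 weeks earlier.

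**Who reads.** Protocol 7.2 says "The investigator will make treatment decisions based on site assessments of scans by RECIST" and "Response and progression will also be assessed by an IRF". Neither document asks for IRF confirmation of PD before scans stop.

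**How the IRF endpoints are censored.** SAP 7.5.3: "Subjects who do not have PD and are still on study at the time of an analysis will be censored" at the last adequate assessment. "Subjects who have started a new anticancer treatment" before documented PD are censored at the last adequate assessment before that treatment. Patients who leave the study without PD are handled in the same way. Death from any cause is otherwise an event. SAP 7.5.5 applies these rules to PFS.

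**What checks are planned.** DOR and PFS per IRF each have one: "A sensitivity analysis to censor subjects who progressed or died after an extended loss to follow up", meaning two or more consecutive missed assessments. SAP 7.5.2.1 plans a concordance summary, but for best overall response only. DOR and PFS per investigator are analysed in parallel.

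**The concern.** A patient whom the investigator calls progressed, but the IRF does not, usually has no further scans on which the IRF could record PD. That patient is then censored in the IRF analysis. Kaplan-Meier estimation assumes that censored patients have the same future risk as those still followed. Patients just called progressed by one reader are plausibly closer than the rest to progression by the other, so censoring them lifts the curve.

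Only one direction of disagreement does this. If the IRF calls PD first, its event is already recorded.

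Protocol 3.2 uses durability to help interpret the ORR, and relies on independent imaging to keep RECIST assessment unbiased in an open-label trial. There is no control arm in which the same bias could cancel. The 6- and 12-month DOR and PFS rates that the SAP will report are directly exposed.

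**Working it through.** **1. The plan's own figures.** The documents give no rate of reader disagreement and no design figure for DOR or PFS. Their power statement concerns ORR only, and it reproduces: with N=100 the exact rule needs 17 responses, and power is 97.9% (stated 98%) at a true 25% and 80.8% (stated 81%) at a true 20%. Nothing below touches it.

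**2. Inputs.**
- From the documents: scans every 8 weeks (Protocol 7.2); one month is 30.4375 days, or 4.348 weeks (SAP 6.4.1); the censoring rules above.
- Assumed: exponential times with median 7.5 months (DOR) or 5.5 months (PFS); 10%, 20% or 30% of patients called PD by the investigator one or two scans before the IRF would; that call must fall on a real scan after the start of the interval; no administrative censoring before 6 months.

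**3. Value if scans continued to IRF PD.** The chance p of PD in one 8-week interval is 1 − exp(−ln 2 × 8 / median in weeks).
- DOR: the median is 7.5 × 4.348 = 32.6 weeks, so p = 0.156.
- PFS: the median is 5.5 × 4.348 = 23.9 weeks, so p = 0.207.

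Six months is 26.1 weeks, so the last scan that counts is at week 24, the third. The estimate is (1 − p)³, which is 0.600 for DOR and 0.499 for PFS.

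**4. Value under the SAP rule, by hand.** Take a lead of one scan and a share d called early. PD found at the first scan cannot have been called earlier, so the first interval is unchanged. At each later scan, a fraction dp of those who would be at risk has already been censored, and the IRF hazard is (1 − d)p / (1 − dp). The 6-month estimate is therefore (1 − p)³ / (1 − dp)².
- DOR: 0.600/0.969 = 0.62, 0.600/0.938 = 0.64, 0.600/0.908 = 0.66 for d = 10%, 20%, 30%.
- PFS: 0.499/0.959 = 0.52, 0.499/0.919 = 0.54, 0.499/0.880 = 0.57.

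**5. Simulation with a lead of one or two scans** (shortened to one where two is impossible):

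| Assumed early calls | 10% | 20% | 30% |
|---|---|---|---|
| 6-month DOR per IRF (60% if scans continued) | 62% | 64% | 66% |
| 6-month PFS per IRF (50% if scans continued) | 52% | 54% | 56% |

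Because first-scan PD is excluded, fewer patients are affected than the nominal share: at 30%, 0.30 × (1 − 0.156) = 25% for DOR and 0.30 × (1 − 0.207) = 24% for PFS. If 30% of the early-called patients die untreated (assumed median 4 months later), the estimates fall by up to about 1 point.

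**6. Does the planned sensitivity analysis show it?** A separate simulation used the protocol scan schedule, a true median PFS of 6 months, 30% early calls one scan ahead, and 30% of those patients dying untreated. The 12-month PFS per IRF is 27.9% if scans continue, 35.1% under the SAP rule, and 35.0% under the planned sensitivity analysis, with unperformed scans after investigator PD treated as missed. The SAP does not say whether they count as missed. The gap of about 7 points stays hidden.

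**7. What would counting investigator PD give?** In the step 5 model it reads about 56% to 59% for DOR and 45% to 48% for PFS, somewhat below the values in step 3.

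**The case against.** The strongest reply has five parts.

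- **Not every such patient is censored.** A reader might infer that investigator PD without IRF PD always ends in censoring. It does not: death without prior new therapy stays an event, though a late one, and an end-of-treatment CT may give the IRF one more scan. Both soften the effect. This stands.
- **The size is easy to overstate.** If early-called patients may be censored at time zero, before any later scan exists, the same assumptions give about 63%, 66% and 69% for DOR and 53%, 56% and 60% for PFS. The scan schedule does not support that: the investigator cannot call radiologic PD before a scan after the start. This stands.
- **An indirect check is planned.** DOR and PFS per investigator are free of this mechanism, and the two curves can be compared. But they change the reader for every patient and, for DOR, also who counts as a responder and from when. A gap between the curves would not show how much comes from censoring. This stands in part.
- **The remedy is not a clean test.** New therapy may start for toxicity or by patient choice, and counting it as PD is pessimistic. This stands, so the result must be labelled a bound.
- **The endpoints are secondary and descriptive.** Protocol 9.3.5.2 plans Kaplan-Meier estimates, with no test or success threshold. This stands and limits the weight of the point.

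**Conclusion.** The gap is real and modest. The stopping rule and the censoring rules together can push DOR and PFS per IRF upward when the investigator calls PD before the IRF would. No planned analysis isolates the effect: the one sensitivity analysis adds censoring, and the concordance summary does not cover PD status or date.

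Under 10% to 30% assumed early calls, the 6-month rates are overstated by about 2 to 6 points, and by up to about 1 point less if some of these patients die untreated. These sizes rest on exponential times, the assumed medians and an assumed rate of disagreement that the documents do not supply. The direction rests on early-called patients being closer to IRF progression than those still followed.

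A reader might infer that the primary result is compromised or that the durability estimates are unusable. The documents support neither: confirmed ORR and its power are untouched, and parallel investigator estimates will be reported. This is a cheap improvement, not a flaw in the primary analysis.

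**What to change.** In SAP 7.5.3 and 7.5.5, keep the main analysis and add, for DOR and PFS per IRF:

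1. A supplementary analysis that counts investigator PD as an event, at its date, where no IRF PD is documented.
2. A second version that also counts the start of new anticancer therapy as an event.
3. A label on both as conservative bounds, not as corrected estimates.
4. A table of IRF against investigator PD status and date, with the number of patients censored for each reason, including those censored after investigator PD.

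Investigator PD and subsequent therapy are already collected, so no scans or visits are added. The cost is a little more analysis work and a supplementary estimate that will be less favourable than the main one.
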